3.5. Safety Review Committee (SRC)

A SRC will be established to assess safety profile for each cohort to determine dose escalation. The SRC will be composed of 3 investigators, the Covance Lead Project Physician, the Gmax Lead Project Physician, and another unblinded physician who is not involved in this study.

SRC Operation. The SRC will meet after 8 of 12 subjects have received 3 doses of the study drug with a 28-day follow-up and the entire cohort of 12 subjects has been randomized.

The initial SRC meeting will review safety data from the initial 8 subjects in Cohort 1 who have completed 3 doses of the study drug and have been followed for 28 days following the third dose. Upon SRC's approval, Cohort 2 will be opened for recruitment once the residual 4 subjects have been randomized in Cohort 1. The second meeting of the SRC will review safety data from the initial 8 subjects in Cohort 2 **and the 4 residual subjects from Cohort 1 who were not yet reviewed.** Upon SRC's approval, once the residual 4 subjects in Cohort 2 are randomized, Cohort 3 can be initiated for recruitment. If fewer than 8 subjects (including 8) in a cohort have completed administration and follow-up regimen, with some drop-outs, their safety data will be reviewed by SRC aiming to determine whether the next cohort with a higher dose can be started. Additionally, ad hoc meetings will be organized in case of any SAE or adverse event with maximum severity that could be drug-related.

SRC reviews will include, but not limited to, clinical findings, vital signs, hematology and biochemistry results, ECG, AEs, and SAEs. The composition, operation, and management of the SRC will be described in detail in the SRC charter.

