3.6. Stopping and Subjects withdraw Criteria

The following criteria will result in immediate discontinuation of the subject dosing:

- An SAE that is related to GMA301;
- QTcF >500 msec or extension 60 msec against baseline.
- Liver function test abnormalities for severe liver injury (based upon US FDA “Guidance for Industry, Drug-Induced Liver Injury: Premarketing Clinical Evaluation”, July 2009):
 - Alanine aminotransferase (ALT) or aspartate aminotransferase (AST)>3x upper limits of normal (ULN) with total bilirubin > 2X ULN (Hy’s Law)
 - ALT or AST >3x ULN with international normalized ratio (INR)>1.5
 - ALT or AST >8X ULN
 - ALT or AST >5X ULN persisting for more than 2 weeks
 - ALT or AST >3x ULN or 3 times baseline value with the appearance of fatigue, nausea, vomiting, right upper quadrant pain or tenderness, fever, rash and/or eosinophilia (>5%)

Close follow-up of subjects must be organized in any of the above cases including:

- Repeating liver enzyme and serum bilirubin tests 2 or 3 times weekly. Frequency of retesting can decrease to once a week or less if abnormalities stabilize or the trial drug has been discontinued and the subject is asymptomatic.
- Obtaining a more detailed history of symptoms and prior or concurrent diseases
- Obtaining a history of concomitant drug use (including non-prescription medications and herbal and dietary supplement preparations), alcohol use, recreational drug use, and special diets.
- Ruling out acute viral hepatitis types A, B, C, D, and E; autoimmune or alcoholic hepatitis; non-alcoholic steatohepatitis; hypoxic/ischemic hepatopathy; and biliary tract disease.
- Obtaining a history of exposure to environmental chemical agents.
- Obtaining additional tests to evaluate liver function, as appropriate (e.g., INR, direct bilirubin)
- Obtaining gastroenterology or hepatology consultations

If a treatment-related SAE is suspected by investigators, immediate discontinuation of study drug must occur and medical care must be applied and the case immediately reported to the SRC. An ad hoc SRC meeting will be organized to make decisions for the study accordingly.

A subject is free to withdraw from the study at any time. A subject is requested to withdraw by the investigators if any of the following criteria are met:

- Subjects' non-compliance with the study procedure that might affect subject safety or study assessments/objectives, by the investigators

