8.6. Safety Analysis

All safety analyses will be performed on the Safety Population. No formal statistical analysis of safety data is planned.

AEs will be coded by System Organ Class and Preferred Term using the current version of the MedDRA dictionary. Safety parameters will be listed and summarized using descriptive statistics. No formal statistical analysis of safety data is planned. Safety data will be summarized by dose group. Incidences of TEAEs (those events that started after exposure to study drug or worsened in severity after dosing) will be presented by dose group as well. Incidences of TEAEs will be presented by maximum severity and relationship to study medication.

Laboratory test results, ECG results, vital sign results and their changes from Baseline will be summarized by dose group using descriptive statistics. Shift tables (low, normal, high) comparing baseline results to the worst post baseline results will be presented by parameters and dose group for laboratory results. Shift tables (normal, abnormal not clinically significant, abnormal clinically significant) comparing baseline results to the worst post baseline results will be presented by parameters and dose group for ECG results. Other safety measurements like physical examinations will be presented in listings.

Prior and Concomitant Medications will be classified according to the WHO Drug Dictionary. All usage will be listed. The current version of the WHO Drug Dictionary will be used. The frequency of usage of each medication class will be summarized using the WHO Drug hierarchy. The percentage of subjects in each dose using each class of medication after baseline will be presented.

The number and percentage of positive ADA and the positive neutralizing antibody at each timepoint will be summarized descriptively.

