10. APPENDICES

Appendix 1: Adverse Event Reporting

Definitions

An AE is any untoward medical occurrence in a subject or clinical investigation subject administered a pharmaceutical product, which does not necessarily have a causal relationship with this treatment. An AE can therefore be any unfavorable and/or unintended sign (including a clinically significant abnormal laboratory finding), symptom, or disease temporally associated with the use of a study drug, whether or not related to the study drug.

Assessment of Severity

The Investigator will be asked to provide an assessment of the severity of the AE using the following categories:

- **Mild:** event is medically significant but produces no disruption to daily activity;
- **Moderate:** event is medically significant and reduces or affects normal daily activity;
- **Severe:** event is medically significant and results in inability to work or perform normal daily activity.

Relationship to Study drug

The Investigator will make a determination of the relationship of the AE to the study drug using a 4-category system according to the following guidelines:

- **Not Related:** The AE is definitely caused by the subject's clinical state or the study procedure/conditions.
- **Unlikely Related:** The temporal association between the AE and the drug is such that the drug is not likely to have any reasonable association with the AE.
- **Possibly Related:** The AE follows a reasonable temporal sequence from the time of drug administration but could have been produced by the subject's clinical state or the study procedures/conditions.
- **Related:** The AE follows a reasonable temporal sequence from administration of the drug, abates upon discontinuation of the drug, follows a known or hypothesized cause-effect relationship, and (if appropriate) reappears when the drug is reintroduced.

Follow-up of Adverse Events

Every reasonable effort will be made to follow up with subjects who have AEs. Any subject who has an ongoing AE that is possibly related or related to the IMP or study procedures at the Follow-up visit will be followed up, where possible, until resolution or until the unresolved AE is judged by the Investigator (or designee) to have stabilized. This will be completed at the Investigator's (or designee's) discretion. Any

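### Appendix 1 grades AE severity only by disruption of daily activity, so an asymptomatic laboratory or ECG abnormality is Mild at any size, which distorts the severity breakdown and misses the severity limb of the ad hoc SRC trigger

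*Combined protocol and SAP*

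**What the plan says.** Section 7.2.1 sends the reader to Appendix 1 for how severity is assigned. Appendix 1 defines an AE broadly, as any unfavorable or unintended sign, "including a clinically significant abnormal laboratory finding". It gives three grades:

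- The lowest grade, Mild, is worded as "event is medically significant but produces no disruption to daily activity".
- The middle grade, Moderate, carries the same condition of medical significance and covers some effect on usual activities.
- The top grade, Severe, is worded as "event is medically significant and results in inability to work or perform normal daily activity".

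The protocol gives no other severity scale, and no numeric grading for laboratory, ECG or vital-sign values.

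Three other sections bear on this scale:

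- Section 3.6 stops a subject's dosing on numeric criteria. One group carries the label "Liver function test abnormalities for severe liver injury" and includes "ALT or AST >8X ULN". QTcF above 500 msec, or 60 msec longer than baseline, is listed separately.
- Section 3.5, on the Safety Review Committee (SRC), says that "ad hoc meetings will be organized in case of any SAE or adverse event with maximum severity that could be drug-related".
- Section 8.6 says that "Incidences of TEAEs will be presented by maximum severity and relationship to study medication". It also makes worsening in severity after dosing one of the two ways in which an event becomes treatment-emergent.

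**The concern.** The scale cannot register how large a laboratory or ECG abnormality is. A finding that causes no symptoms does not disrupt daily activity, so it lands in the lowest grade however extreme the value. The same ALT result is then severe liver injury under 3.6 and Mild under Appendix 1.

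Two uses of the grade are exposed. The severity table in 8.6 is where a reader of a safety study looks for the serious end of the AE profile. The ad hoc trigger in 3.5 is the only stated route by which one non-serious event convenes the committee between scheduled reviews. The protocol's Introduction names hepatotoxicity and anemia among the safety concerns of existing endothelin receptor antagonists, and both are usually found by blood test.

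**Working it through.** There is no plan figure to reproduce. The check applies the three definitions literally and follows the resulting grade through the sections that use it.

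**Step 1: what separates the grades.** All three require medical significance, so that element separates nothing. What remains is no disruption, some effect on activity, or inability to work or carry on normal activity. Size of abnormality plays no part.

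**Step 2: apply this to the section 3.6 criteria.**

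| 3.6 criterion | Symptom needed? | Grade if asymptomatic |
|---|---|---|
| ALT or AST >3x ULN with total bilirubin >2x ULN | No | Mild |
| ALT or AST >3x ULN with INR >1.5 | No | Mild |
| ALT or AST >8x ULN | No | Mild |
| ALT or AST >5x ULN for more than 2 weeks | No | Mild |
| ALT or AST >3x ULN or 3 times baseline, with listed symptoms, signs or eosinophilia | Usually | Depends on the symptom |
| QTcF >500 msec | No | Mild |
| QTcF 60 msec above baseline | No | Mild |

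So 4 of 5 hepatic criteria and 2 of 2 QTcF criteria can be met by an event graded Mild.

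**Step 3: follow the grade.**

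- *TEAE incidence (2.2.1).* Severity is not part of the endpoint. A new-onset event counts once whatever its grade.
- *TEAE definition (8.6).* Exclusion criterion 13a admits subjects with ALT or AST above normal but below 2 times ULN. If such a value rises above 8 times ULN without symptoms, the scale offers only Mild before and Mild after, so the worsened-in-severity rule may not register the change. This is conditional: 7.2.1 records non-serious AEs only from the start of study drug, so a site may enter the rise as a new event, and it would then count.
- *Maximum-severity table (8.6).* The event appears as Mild. The laboratory shift tables do not correct this. Their categories are low, normal and high, so 1.1 and 9 times ULN (illustrative values) share a cell.
- *Ad hoc SRC trigger (3.5).* Maximum severity is not defined there. Read against the only scale given, it means Severe. A non-serious, asymptomatic event meets neither limb.
- *Cohort stopping (3.6).* One criterion refers to increased severity of known and expected AEs, so it draws on the same scale.

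**Step 4: how long the scheduled route takes.** The first SRC review needs 8 subjects with three doses and 28 days of follow-up. The third dose is at Week 8, and 28 days is 4 weeks, so an individual subject reaches that point at 8 + 4 = Week 12. A finding at a subject's Week 4 visit therefore waits at least 12 − 4 = 8 weeks if all eight enter together, and longer with staggered entry. Section 3.5 spells out a first and a second meeting, covering Cohorts 1 and 2, and does not set one out by name for Cohort 3.

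**The case against.** The strongest reply is that little depends on the grade.

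- *The primary endpoint.* A reader might infer that the primary result is understated. The documents do not support that: the endpoint is incidence, and new-onset events count at any grade.
- *Subject protection.* A reader might infer that a subject with a Mild ALT above 8 times ULN stays on drug. That is wrong. Section 3.6 stops dosing on the number and requires close follow-up of the liver criteria. Section 7.2.4.1 separately holds drug on QTcF.
- *Visibility.* The signal is not hidden. Section 8.1 provides by-subject listings and continuous summaries that include the maximum, which would show an extreme value among 9 active subjects per cohort. The ECG shift tables in 8.6 have a clinically significant category.
- *The committee.* The SRC can still be reached if the investigator judges the event an important medical event and hence serious, after two drug-related discontinuations in a cohort, or at scheduled review, which covers biochemistry and ECG whatever the grade.
- *Absent documents.* The SRC charter cited in 3.5 and the separate analysis plan cited in 8.1 are not in the text reviewed. Either could define maximum severity or add grading.
- *Prior evidence.* The Introduction says ambrisentan and macitentan have not shown strong evidence of hepatotoxicity in trials. The monkey studies in 1.3 report no clinical chemistry changes.

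All of this stands, and it limits the point without removing it. Other displays do not make the severity table right. The serious-event route is discretionary, the discontinuation rule needs a second case, and the scheduled route takes time. None guarantees an ad hoc meeting for one non-serious case. Because 7.2.1 places severity assignment in Appendix 1, that is where the rule belongs.

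**Conclusion.** The point holds within limits. Appendix 1 and section 3.6 classify the same asymptomatic finding at opposite ends, and the lower classification feeds the 8.6 severity table and the severity limb of the 3.5 trigger. The oversight gap is narrow: a single non-serious, asymptomatic, possibly drug-related case, which may wait for scheduled review. A worsening pre-existing abnormality may also escape the TEAE definition.

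No rate can be attached to this. One event in a 9-subject arm is 1/9 = 11%, but that only divides a hypothetical event by the arm size and says nothing about how often it will occur.

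The medical-significance wording is a lesser matter. Read literally, a brief headache fits no grade, but 7.2.1 requires all non-serious AEs to be recorded after the start of study drug, so no event is lost.

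The conclusion assumes that maximum severity in 3.5 means Severe in Appendix 1, and that neither the charter nor the analysis plan supplies another scale. It should be corrected, but it does not undermine the primary endpoint or individual stopping.

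**What to change.** In Appendix 1:

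1. Keep the activity-based grades for symptomatic AEs.
2. State that AEs defined by laboratory, ECG or vital-sign values are graded by magnitude on a published toxicity scale, chosen and named by the sponsor.
3. As a tidy-up, remove the medical-significance condition from the three grades.

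Then reconcile Appendix 1 with 3.5, 3.6 and 8.6, and say in 3.5 what maximum severity means, so that the severity table and the SRC trigger use a scale that can register these findings.

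Giving the top grade to anything that meets a 3.6 criterion is a tempting shortcut. It would turn stopping rules into severity grades: a QTcF rise from 380 to 441 msec (illustrative), which is 61 msec, would become Severe. It would also alter a safety-oversight trigger indirectly. Which thresholds apply is for the sponsor to decide.

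The cost is wording in Appendix 1 and the matching eCRF guidance, with no extra data collection. Some laboratory or ECG AEs will move to a higher grade, and a few more ad hoc SRC meetings may follow.

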Appendix 2: Clinical Laboratory and other Evaluations

Clinical chemistry:	Hematology:	Urinalysis:
Alanine aminotransferase Albumin Alkaline phosphatase Aspartate aminotransferase Blood urea nitrogen Calcium Chloride Cholesterol Creatinine Gamma-glutamyl transferase Glucose Potassium Sodium Total bilirubin ^a Total protein Uric acid	Hematocrit Hemoglobin Mean cell hemoglobin Mean cell hemoglobin concentration Mean cell volume Platelet count Red blood cell (RBC) count White blood cell (WBC) count WBC differential: Basophils Eosinophils Lymphocytes Monocytes Neutrophils Coagulation profile: Activated partial thromboplastin time International normalized ratio Prothrombin time	Bilirubin Blood Color and appearance Glucose Ketones Leukocyte esterase Nitrite pH Protein Specific gravity Urobilinogen
Serology^b:	Drug screen	Hormone panel - females only:
Hepatitis B surface antigen Hepatitis C antibody Human immunodeficiency - antibodies	Not applicable	Follicle-stimulating hormone ^b (postmenopausal females only) Serum or Urine pregnancy test ^c

^a Direct and indirect bilirubin will be analyzed if total bilirubin is elevated

^b Only analyzed at Screening.

^c All females will perform pregnancy test in serum at Screening and in urine at all other times.

Appendix 3: Total Blood Volume

The following blood volumes will be withdrawn for each subject.

	Volume per blood sample (mL)	Maximum number of blood samples	Total amount of blood (mL)
Hematology, clinical chemistry, and coagulation	10	5	50
Serology	5	1	5
GMA301 pharmacokinetics	2	21	42
ADA	6	6	36
NT-proBNP	2.5	4	10
FSH and pregnancy test	5	1	5

Blood volumes for clinical chemistry, hematology, coagulation, serology test, FSH, and pregnancy test will meet local laboratory requirement. The volumes in above table are only for reference.

Appendix 4: Contraception Guidance

Definitions

Women of Childbearing Potential: premenopausal females who are anatomically and physiologically capable of becoming pregnant following menarche.

Women of Nonchildbearing Potential:

1. **Surgically sterile:** females who are permanently sterile via hysterectomy, bilateral salpingectomy, and/or bilateral oophorectomy by reported medical history and/or medical records. Surgical sterilization to have occurred a minimum of 6 weeks, or at the Investigator's discretion, prior to Screening.
2. **Postmenopausal:** Females at least 45 years of age with amenorrhea for 12 months without an alternative medical reason with confirmatory follicle-stimulating hormone (FSH) levels of ≥ 40 mIU/mL. The amenorrhea should not be induced by a medical condition such as anorexia nervosa, hypothyroid disease or polycystic ovarian disease, or by extreme exercise. It should not be due to concomitant medications that may have induced the amenorrhea such as oral contraceptives, hormones, gonadotropin-releasing hormones, anti-estrogens, or selective estrogen receptor modulators.

Fertile male: a male that is considered fertile after puberty.

Infertile male: permanently sterile male via bilateral orchiectomy.

Contraception Guidance

Female Subjects

Female subjects who are of nonchildbearing potential will not be required to use contraception. Female subjects of childbearing potential must be willing to use an acceptable method of birth control from the time of signing the informed consent form until 90 days after the Follow-up visit. Acceptable methods of contraception include:

- hormonal injection (as prescribed)
- combined oral contraceptive pill or progestin/progestogen-only pill (as prescribed)
- combined hormonal patch (as prescribed)
- combined hormonal vaginal ring (as prescribed)
- surgical method performed at least 3 months prior to the Screening visit:
 - bilateral tubal ligation
 - Essure® (hysteroscopic bilateral tubal occlusion) with confirmation of occlusion of the fallopian tubes
- hormonal implant

- hormonal or non-hormonal intrauterine device
- male condom with spermicide
- female condom with spermicide
- over-the-counter sponge with spermicide
- cervical cap with spermicide (as prescribed)
- diaphragm with spermicide (as prescribed)
- vasectomized male partner (sterilization performed at least 90 days prior to the Screening visit, with verbal confirmation of surgical success, and the sole partner for the female subject).

Female subjects of childbearing potential should refrain from donation of ova from Check-in (Day -1) until 90 days after the Follow-up visit.

Male Subjects

Male subjects will be surgically sterile for at least 90 days, with documented azoospermia, or when sexually active with female partners of childbearing potential will be required to use a male condom with spermicide (even if participant has a history of vasectomy) from Check-in until 90 days after the Follow-up visit. Sexual intercourse with female partners who are pregnant or breastfeeding should be avoided unless condoms are used from the time of the first dose until 90 days after the Follow-up visit. Male subjects are required to refrain from donation of sperm from Check-in until 90 days after the Follow-up visit.

Sexual Abstinence and Same-sex Relationships

Subjects who practice true abstinence, because of the subject's lifestyle choice (ie, the subject should not become abstinent just for the purpose of study participation), are exempt from contraceptive requirements. Periodic abstinence (eg, calendar, ovulation, symptothermal, postovulation methods) and withdrawal are not acceptable methods of contraception. If a subject who is abstinent at the time of signing the ICF becomes sexually active they must agree to use contraception as described previously.

For subjects who are exclusively in same-sex relationships, contraceptive requirements do not apply. If a subject who is in a same-sex relationship at the time of signing the ICF becomes engaged in a heterosexual relationship, they must agree to use contraception as described previously.

Appendix 5: Regulatory, Ethical, and Study Oversight Considerations

Regulatory and Ethical Considerations

This study will be conducted in accordance with the protocol and with the following:

Consensus ethical principles derived from international guidelines including the declaration of Helsinki and Council for International Organizations of Medical Sciences (CIOMS) International Ethical Guidelines.

Applicable ICH Good Clinical Practice (GCP) Guidelines.

Applicable laws and regulations.

The protocol, protocol amendments, ICF, Investigator Brochure, and other relevant documents must be submitted to an IRB/Ethics Committee (EC) by the Investigator and reviewed and approved by the IRB/EC before the study is initiated.

Any amendments to the protocol will require IRB and regulatory authority (as locally required) approval before implementation of changes made to the study design, except for changes necessary to eliminate an immediate hazard to study subjects.

The Investigator will be responsible for the following:

Providing written summaries of the status of the study to the IRB/EC annually or more frequently in accordance with the requirements, policies, and procedures established by the IRB/EC.

Notifying the IRB/EC of SAEs or other significant safety findings as required by IRB/EC procedures.

Providing oversight of the conduct of the study at the site and adherence to requirements of 21 Code of Federal Regulations (CFR), ICH guidelines, the IRB/EC, European regulation 536/2014 for clinical studies (if applicable), and all other applicable local regulations.

Finances and Insurance

Financing and insurance will be addressed in a separate agreement.

Informed Consent

Prior to starting participation in the study, each subject will be provided with a study-specific ICF giving details of the study drugs, procedures, and potential risks of the study. Subjects will be instructed that they are free to obtain further information from the Investigator (or designee) and that their participation is voluntary, and they are free to withdraw from the study at any time. Subjects will be given an opportunity to ask questions about the study prior to providing consent for participation.

Following discussion of the study with Clinical Research Unit personnel, subjects will sign 2 copies of the ICF in the presence of a suitably trained member of staff to indicate that they are freely giving their informed consent. One copy will be given to the subject, and the other will be maintained in the subject's records.

Subjects must be re-consented to the most current version of the ICF(s) during their participation in the study.

Subject Data Protection

Subjects will be assigned a unique identifier and will not be identified by name in eCRFs, study-related forms, study reports, or any related publications. Subject and Investigator personal data will be treated in compliance with all applicable laws and regulations. In the event the study protocol, study report, or study data are included in a public registry, all identifiable information from individual subjects or Investigators will be redacted according to applicable laws and regulations.

The subject must be informed that his/her personal study-related data will be used by the Sponsor in accordance with local data protection law. The level of disclosure must also be explained to the subject. The subject must also be informed that his/her study-related data may be examined by Sponsor or CRO auditors or other authorized personnel appointed by the Sponsor, by appropriate IRB/EC members, and by inspectors from regulatory authorities.

Disclosure

All information provided regarding the study, as well as all information collected and/or documented during the course of the study, will be regarded as confidential. The Investigator (or designee) agrees not to disclose such information in any way without prior written permission from the Sponsor.

Data Quality Assurance

The following data quality steps will be implemented:

All relevant subject data relating to the study will be recorded on eCRFs unless directly transmitted to the Sponsor or Covance electronically (eg, laboratory data). The Investigator is responsible for verifying that data entries are accurate and correct by electronically signing the eCRF.

The Investigator must maintain accurate documentation (source data) that supports the information entered in the eCRF.

The Investigator must permit study-related monitoring, audits, IRB/EC review, and regulatory agency inspections and provide direct access to source data documents.

The Sponsor or Covance is responsible for the data management of this study including quality checking of the data. Predefined agreed risks, monitoring thresholds, quality tolerance thresholds, controls, and mitigation plans will be documented in a risk management register. Additional details of quality checking to be performed on the data may be included in a Data Management Plan.

A Study Monitor will perform ongoing source data verification to confirm that data entered into the eCRF by authorized site personnel are accurate, complete, and verifiable from source documents; that the safety and rights of subjects are being protected; and that the study is being conducted in accordance with the currently approved protocol and any other study agreements, ICH GCP, and all applicable regulatory requirements.

Records and documents, including signed ICFs, pertaining to the conduct of this study must be retained by the Investigator in accordance with 21 CFR 312.62(c) (US site) unless local regulations or institutional policies require a longer retention period. No records may be destroyed during the retention period without the written approval of the Sponsor. No records may be transferred to another location or party without written notification to the Sponsor.

Investigator Documentation Responsibilities

All individual, subject-specific study data will also be entered into a 21 CFR Part 11-compliant electronic data capture (EDC) system on an eCRF in a timely fashion.

All data generated from external sources (eg, laboratory and bioanalytical data), and transmitted to the Sponsor or Covance electronically, will be integrated with the subject's eCRF data in accordance with the Data Management Plan.

An eCRF must be completed for each enrolled subject who undergoes any screening procedures, according to the eCRF completion instructions. The Sponsor, or CRO, will review the supporting source documentation against the data entered into the eCRFs to verify the accuracy of the electronic data. The Investigator will ensure that corrections are made to the eCRFs and that data queries are resolved in a timely fashion by the study staff.

The Investigator will sign and date the eCRF via the EDC system's electronic signature procedure. These signatures will indicate that the Investigator reviewed and approved the data on the eCRF, data queries, and site notifications.

Publications

If on completion of the study the data warrant publication, the Investigator may publish the results in recognized (refereed) scientific journals subject to the provisions of the clinical study agreement (CSA). Unless otherwise specified in the CSA, the following process will occur:

If the Investigator expects to participate in the publication of data generated from this site, the institution and Investigator will submit reports, abstracts, manuscripts, and/or other presentation materials to the Sponsor for review before submission for publication or presentation. The Sponsor will have 60 days to respond with any requested revisions including, without limitation, the deletion of confidential information. The Investigator will act in good faith upon requested revisions, except the Investigator will delete any confidential information from such proposed publications. The Investigator will delay submission of such publication or presentation materials for up to an additional 90 days in order to have a patent application(s) filed.

